2.2 Objectives

Our objectives are:

1. To adapt the existing *Five ways to wellbeing* course for adults to a school setting, and to pilot the intervention in two schools.
2. To explore how participating pupils, teachers, and other school personnel experience the pilot intervention, and identify aspects that should be adjusted before proceeding to a full scale trial.
3. To examine how the teachers deliver the intervention in the full scale trial; their motivation, obstacles they encounter, general satisfaction with the intervention, and their adherence to the intervention manual (i.e., fidelity).
4. To investigate whether the intervention is acceptable and experienced as useful for participating school pupils, parents, teachers, and other school personnel.
5. To investigate whether the intervention have any adverse effects, such as triggering negative emotions.
6. To evaluate the process of implementation.
7. To describe the pupils' wellbeing and mental health at baseline (November 2023).

8. To examine the immediate and long-term effects of the intervention on the pupils' wellbeing and mental health.
9. To assess for whom the intervention is effective (i.e., subgroup analysis and moderation analysis, for example SES, gender, baseline symptom levels, etc.).
10. To investigate what mechanisms explain potential improvements in wellbeing after exposure to the interventions.

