2.3 Trial design

In phase 1, we will conduct a pilot study in two chosen schools in Råde Municipality.

In phase 2, we will use the quasi-experimental Extended Selection Cohorts (ESC) design. The ESC design is an option for real-life settings when an RCT is not feasible, because the ESC design makes it possible to compare same-age treatment groups. For the current study, a cluster-RCT of sufficient power would have needed a large number of schools and is therefore not feasible. The ESC design is a cohort-longitudinal design with adjacent cohorts, that are measured at two or more time points; a design that has been used to evaluate effects of school-based interventions, for example anti-bullying programmes (Kärnä et al., 2011; Olweus, 2005) and a programme that promotes physical activity and a healthy diet (Takens et al., 2020). Each cohort comprises subjects of approximately the same age. In a standard RCT design, the pupils, classes, or schools are randomly allocated to different intervention and control groups; but in the ESC design intervention and control groups belong to the same schools, and fewer schools or pupils are therefore needed. The cohorts that are exposed to the intervention are compared with unexposed cohorts from the same school, ensuring that the research subjects are recruited from a relatively stable population with the same socio-demographic characteristics (Olweus, 2005; Takens et al., 2020). This is important when studying health and health behaviour, which differs according to different SES and ethnicity groups. The ESC design does not, however, allow us to control for general societal time trends that coincide with the intervention.

In our study, we will collect data from each cohort (i.e., school grade) five times, starting in November, 2023 (baseline), followed by January, February, March, and November, 2024.

At 12 months follow-up, each cohort will be compared to the same-age adjacent baseline cohort group (see Figure 1). For instance, the measures of the grade 5 cohorts that will have been *exposed* to the intervention (grade 5 in 2024–2025) will be compared to the baseline measures of the *unexposed* grade 5 cohorts (grade 5 in 2023–2024).

Figure 1. How exposed cohorts can be compared to unexposed cohorts at 12 months follow-up

	Cohort A	Cohort B	Cohort C	Cohort D	Cohort E	Cohort F
Baseline (Nov. 2023)	Grade 5	Grade 6	Grade 7	Grade 8	Grade 9	Grade 10
Intervention						

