Follow-up (Nov. 2024)	Grade 6	Grade 7	Grade 8	Grade 9	Grade 10	

In order to separate any effects of the intervention from changes in variables due to other causes, we will apply a «wait list control group» element, i.e., delayed intervention: approximately $\frac{1}{2}$ of the schools will start the intervention in November 2023, while the remaining schools will start the intervention approx. 14 weeks later. We will collect data from all pupils in November 2023, and in February 2024 we will compare the scores of the intervention group with the «wait list» group.

3 Methods

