3.11 Statistical Analysis Plan

To analyse the effect of the intervention we will use multilevel regression. In these analyses individual measurements at the five timepoints are nested within pupils (level 2), which in turn are nested within classes (level 3), in turn nested within schools (level 4). We will use linear multilevel regression for all continuous outcome measures, and logistic multilevel regression for categorical outcome variables.

Multilevel models are ideally suited for clustered and longitudinal data, where the common assumption of independence of measures does not hold. The models also perform well with missing data, and can be used to investigate both general trends, and factors underlying the variability observed at various levels in the hierarchy.

Based on previous research we hypothesize that the effects of the intervention will be greater for individuals who score lower on wellbeing measures and/or higher on mental health symptoms at baseline. We will therefore stratify our sample based on the participants' wellbeing scores and their mental health symptoms score and perform subgroup analysis. We also hypothesize that the effects of the intervention will be greater for younger participants, and we will therefore perform subgroup analysis based on school grade (as a proxy for participants' age).

To explore the moderation effects by SES, gender, age in years, ethnicity, baseline level of mental health symptoms, loneliness, wellbeing level, and leisure activities level, we will add interaction terms to the model. When these terms are significant, we will stratify the analyses for specific subgroups.

A significance level of $p = 0.05$ will be used. For the analyses we will use Stata v. 18, IBM SPSS Statistics v. 25.0, and R 3.5.3.

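### No primary outcome, time point or contrast is designated, no multiplicity rule is stated, and the quoted power of 0.8411 fits neither planned comparison

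*Combined protocol and SAP*

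**What the plan says.** **Objective and outcomes.** Objective 8 in Section 2.2 is "To examine the immediate and long-term effects of the intervention on the" pupils' wellbeing and mental health. Sections 3.4.1 to 3.4.5 list life satisfaction (present, expected, by domain), friendship, loneliness, depressive symptoms, prosocial behaviour, leisure activities and screen time. No outcome is ranked above another.

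**Contrasts.** Section 2.3 gives two.
- Adjacent cohorts: "At 12 months follow-up, each cohort will be compared to the same-age adjacent baseline cohort group".
- Delayed start: about half "of the schools will start the intervention in November 2023, while the remaining schools will start the intervention approx. 14 weeks later", and the two groups are compared in February 2024.

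Neither is called primary.

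**Analysis.** Section 3.11 states "We will use linear multilevel regression for all continuous outcome measures, and logistic multilevel regression for categorical outcome variables". Repeated measurements are nested in pupils, pupils in classes, and classes are "in turn nested within schools (level 4"). The section does not say which model term tests the effect. The only rule for inference is "A significance level of $p = 0.05$ will be used". The same section plans to stratify by participants' "wellbeing scores and their mental health symptoms score and perform subgroup analysis", plans subgroups by grade, and adds interaction terms for a list of moderators, with stratification where a term is significant.

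**Power.** Section 3.7 uses an online two-arm cluster calculator with 157 classes, 15 pupils per class, effect size 0.16, intraclass correlation 0.05 and a two-sided 0.05 level, and reports 0.8411. It names no outcome, wave or contrast.

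**The concern.** If the plan is followed as written, no single test answers whether the programme works. Each outcome can be tested at 0.05 at either contrast, so a favourable result can be found somewhere by chance more often than 5% of the time.

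The two contrasts also have different weaknesses and may disagree. Of the adjacent-cohort comparison, Section 2.3 says: "The ESC design does not, however, allow us to control for general societal time trends that coincide with the intervention". The February comparison is not described as randomised. If they point in different directions, the plan has no rule for which one decides. Nor can a reader tell which result the 84% power supports.

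**Working it through.** **1. Reproduce the stated power.** Inputs from Section 3.7: J = 157 classes, m = 15, d = 0.16, ICC = 0.05, two-sided 0.05.

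- Variance of the difference = 4 × (0.05 + 0.95/15)/157 = 0.002887; standard error 0.05374.
- Noncentrality = 0.16/0.05374 = 2.978, on 157 − 2 = 155 df.
- Power (noncentral t) = 0.8411, which agrees with the plan.

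**2. Compare that layout with the two contrasts.**

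- *February 2024.* Schools, not classes, start early or late (Section 2.3). Section 2.1 gives 16 schools. The calculation has no school component, although Section 3.11 models schools as level 4.
- *12 months.* In Figure 1, cohorts B to E each appear twice: as the unexposed baseline comparator for the cohort below, and as an exposed cohort at follow-up. The two sides share pupils and schools, so they are not independent arms.

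**3. Illustrate February power.** Assumptions not in the documents: a school ICC s inside the total of 0.05, 8 schools per group, equal school sizes, 16 − 2 = 14 df, and a baseline correlation of 0.6 where adjustment is shown.

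Variance = 4 × [s/16 + (0.05 − s)/157 + 0.95/(157 × 15)]

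Example, s = 0.01: 4 × (0.000625 + 0.000255 + 0.000403) = 0.00513; standard error 0.0716; noncentrality 2.233; power 55%.

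For baseline adjustment, the lower figure multiplies only the pupil term by 1 − 0.6² = 0.64; the upper figure multiplies the whole variance by 0.64.

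| Assumed school ICC | Unadjusted, 14 df | Unadjusted, 155 df | Baseline-adjusted, 14 df |
|---|---|---|---|
| 0 | 79% | 84% | 87–93% |
| 0.005 | 65% | 71% | 72–84% |
| 0.01 | 55% | 60% | 60–74% |
| 0.02 | 41% | 46% | 44–58% |

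At s = 0 the fall from 84% to 79% comes only from the degrees of freedom.

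**4. Illustrate the false-positive rate.** One contrast, no true effect, k scores with common correlation ρ, each tested two-sided at 0.05. With Φ and φ the standard normal distribution function and density:

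P(at least one) = 1 − ∫ φ(u) {Φ[(1.96 − √ρ u)/√(1 − ρ)] − Φ[(−1.96 − √ρ u)/√(1 − ρ)]}^k du

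At ρ = 0 this is 1 − 0.95^k.

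| k (assumed) | ρ = 0 | 0.3 | 0.5 | 0.7 |
|---|---|---|---|---|
| 5 | 23% | 21% | 18% | 15% |
| 10 | 40% | 35% | 29% | 21% |

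The five are present, expected and domain life satisfaction, depressive mood and prosocial behaviour. The ten add trusted friend, friend to be with, loneliness, weekly leisure, and daily leisure with screen time. Some of these composites are mine, not the plan's. Counting each item or established scale in Sections 3.4.1 to 3.4.4 separately (2 Cantril ratings + 6 domains + 3 friendship items + loneliness + depression + prosocial = 14) gives 1 − 0.95^14 = 51% under independence, so the figure depends heavily on how items are scored.

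**5. 12-month power.** The documents give no correlation between waves within pupils or between cohorts within a school, so I give no figure.

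**The case against.** Several points on the other side stand and limit the claim.

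- *Contrasts and time points are described.* A reader might infer that the plan has none. It has two; the gap is that neither is designated primary or linked to the power calculation.
- *Lack of adjustment is inferred.* The plan does not rule out a correction; it states one level and mentions none.
- *Low power is not shown.* A reader might take the February figures as proof that the study is underpowered. They rest on an assumed school ICC and 14 df, which the SAP does not specify. The unadjusted column also ignores the baseline wave that the planned longitudinal model would use. With adjustment the range, 44 to 93%, spans 84%.
- *The design is named after the adjacent-cohort comparison,* and the wait list is an added element. The missing school clustering is therefore shown to matter only if February is chosen. For 12 months the problem is overlap between the cohorts, which I have not quantified.
- *Moderators are tested.* A reader might infer that the subgroups by baseline score and grade have no interaction test. Section 3.11 plans interaction terms for age, baseline symptoms and wellbeing level, and already frames moderation as exploratory. What is unclear is whether the stratified analyses wait for those tests.
- *Some scores are defined.* The depression inventory has six items, the prosocial measure five, and each Cantril rating and loneliness is one item. The gap is confined to the life-domain, friendship and leisure items and to what counts as a wellbeing score.

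The plan cannot be excused as wholly exploratory: Section 3.11 does not label the effect analysis so, and Section 3.7 computes power for a hypothesis test.

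**Conclusion.** The concern holds in this form: no outcome, time point or contrast is designated primary, a single 0.05 level covers all outcomes with no multiplicity rule, and 0.8411 is a correct calculation for a layout that matches neither planned comparison.

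The omissions are read directly from the text. The sizes are illustrations: about 15 to 40% for at least one false positive at one contrast, and February power of 79 to 41% unadjusted or 93 to 44% adjusted. They depend on the assumed number of scores, their correlation, the school ICC, the degrees of freedom and the baseline correlation. The documents do not support saying that the stated power is miscalculated or that true power is below 84%. The data remain usable; what is undefined is the confirmatory claim.

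**What to change.** Before outcome analysis:

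1. Name one primary outcome, time point and contrast, tested at two-sided 0.05, and justify the choice. Section 3.5 places data collection in November 2023 to November 2024; if the choice is made after that, disclose it, because it is weaker than a choice made in advance.
2. In the justification, acknowledge that the 12-month comparison cannot separate the programme from societal trends and that the February comparison is not described as randomised. Confirm that the second group was still unexposed when measured in February: 14 weeks (98 days) after 1 to 30 November 2023 is 7 February to 7 March 2024.
3. Apply a multiplicity procedure, for example Holm, to a short named list of secondary outcomes. Label the remaining outcomes, waves and subgroup analyses exploratory.
4. State how the life-domain, friendship and leisure items, and the wellbeing scores used for stratification, are formed.
5. State whether the subgroup analyses by baseline score and grade are unconditional or follow the interaction tests.
6. Restate power for the chosen contrast. For February, use schools as the allocated clusters, with baseline adjustment and a range of school ICCs. For 12 months, account for overlapping cohorts within the same schools.

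The cost is SAP wording and one new power calculation, with no new data. The price is less power to claim secondary effects and possibly a lower stated power.

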3.12 Qualitative Analysis

Researchers will take written notes during the focus group interviews, and we will conduct a content analysis by two independent researchers. At first, the researchers will do the analysis independently; then their analyses will be compared and consensus will be reached.

4 Ethics and dissemination

4.1 Potential harms and benefits for the participants

The *5Ways@School* intervention will be built from existing teaching material currently used among adults at Norwegian Healthy Lifestyle Centres. Experiences from teaching the Five Ways to Well-being at Healthy Lifestyle Centres have been positive, and no harm among adult participants has been reported. To our knowledge, no harm has been reported when using the Five Ways among children and youth in other countries. Based on former studies, we expect the participants to experience benefits from the intervention, and we believe the risk of adverse reactions to the teaching programme is very low. Likewise, we believe the risk of adverse reactions to the questionnaires is similarly low. Nevertheless, we will investigate whether some pupils can have negative reactions, either to the teaching programme or the questionnaires, and we will provide them with support from the teacher or the school nurse if needed. The teachers who administer the intervention, who know the pupils in their class well, will identify if pupils need further support and will refer them to school nurses if needed.

Teachers who deliver the intervention will be invited to complete questionnaires, and some teachers, school nurses, school leaders, and parents will be invited to participate in focus group interviews. We do not consider such participation to be harmful.

In total, we consider the cost-benefit ratio to be favourable for all participants.

4.2 Research ethics approval

Ethical approval is obtained by the Regional Ethic Committee (reference number 491440).

4.3 Protocol amendments

Important protocol modifications will be communicated from the PI to the Head of education in Moss, who will inform affected pupils, parents, and teachers. Likewise, the PI will inform the team of supervisors, contributing organisations, and other stakeholders.

4.4 Consent or assent

In the first (pilot) phase of the study, no information will be collected from the pupils taking part in the pilot. At the end of each pilot teaching session, we will ask the teachers to give us feedback on what parts of the teaching session went well and what parts should be adjusted.

In phase two of the study, informed consent will be sought from the parents before the pupils are invited to complete questionnaires. Consent from one parent will be considered adequate. If a pupil has one consenting parent and one assenting, the assenting parent will be respected and the pupil will not participate. Given consent from their parent(s), the pupils will be invited to participate and asked for informed consent. Parents and/or pupils may at any timepoint choose to withdraw their consent, and we will then delete the information we have collected from the pupil in question. The right to claim deletion of information does not apply to data that has been entered into statistical analyses.

The teachers who give the teaching in *5Ways@School* will be invited to complete a questionnaire. The participation of the teachers is voluntary and based on informed consent. The teachers may at any timepoint choose to withdraw their consent, and we will then delete the information we have collected from the pupil in question. The right to claim deletion of information does not apply to data that has been entered into statistical analyses.

Before focus group interviews we will give written information to participants, stating that participating is voluntary and that they may choose not to participate. As stated earlier, only adults will be invited to focus group interviews.

4.5 Confidentiality

The participants' confidentiality will be protected by strict procedures, ensuring that personal information will be de-identified. By de-identified, we refer to data where personal identifying information is removed. To prevent the possibility of data re-identification, school name and school class membership will not be included in the final dataset (only gender and school grade). Data will not be disclosed to others or transferred to countries outside of Norway.

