3.7 Sample size

During the study period, there will be approximately 3,300 pupils in grade 5 to 10 in the public schools in Moss, who will be invited to participate. We have a conservative estimate of 70 % participation, i.e., about 2,300 participants. All pupils in 157 school classes in Moss municipality will be invited to participate in our study. The average number of pupils in a school class in Moss is 21, and we assume that 15 pupils per class (i.e., 70 %) participate.

Estimating statistical power in a clustered trial that is not randomized can be challenging, as we need to account for the correlation within clusters and the variation between clusters, as well as the variation in the outcome measure(s). Our approach to determine statistical power was to run a power analysis available at <http://psychstat.org/crt2arm> with the following assumptions:

- Sample size (i.e., number of participating pupils per class): 15
- Effect size: 0.16
- Number of clusters (i.e., number of school classes); 157
- Intra-class correlation: 0.05

- Significance level: 0.05
- Power curve: No power curve
- H1: Two-sided test

This analysis resulted in a power of 0.8411. The assumption that our intervention might have an effect size of 0.16 is based on previous studies, see (Tanner-Smith et al., 2018; Taylor et al., 2017; Werner-Seidler et al., 2017).

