3.10 Data management

Data will be stored and analysed in TSD, which is a platform for collecting, storing, analysing and sharing sensitive data in compliance with the Norwegian privacy regulation. TSD offers virtual servers and backup- and storage systems with very high safety standards.

Students and teachers will be invited sign in through their digital Feide school account. Feide is the national solution for secure login and data sharing in education and research in Norway.

With Feide, pupils, students, researchers and teachers get safe and correct access to a number of different digital services with one username and password. TSD will ensure that every Feide username will be automatically encrypted with an encryption key unique to this project, and the encrypted username will act as the student’s or teacher’s serial number in the data file. The data file is located on a secure server at TSD and will not contain identifiers such as names, Feide usernames or national ID numbers. The project manager and staff (named in point 1.7) will be given access to the data file to analyse data on TSD’s server. The researchers will not be able to identify individual students or teachers on the basis of the data file.

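### Section 4.5 strips class membership from the final dataset, but the analysis model needs class as a level, and nothing says that class, school or start-group codes are kept

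*Combined protocol and SAP*

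**What the plan says.** - **Section 4.5 (Confidentiality):** to guard against re-identification, "school name and school class membership will not be included in the final dataset (only gender and school grade".
- **Section 3.11 (Statistical Analysis Plan):** the effect analysis is a four-level regression, with measurements within pupils, "which in turn are nested within classes (level 3), in turn nested within schools (level 4".
- **Section 3.7 (Sample size):** the power calculation rests on "Number of clusters (i.e., number of school classes); 157", with 15 pupils per class and an intra-class correlation of 0.05.
- **Section 2.3 (Trial design):** start group is set by school. About half the schools begin in November 2023 and "the remaining schools will start the intervention approx. 14 weeks later". The wait-list contrast follows: "in February 2024 we will compare the scores of the intervention group" with that of the schools still waiting. The 12-month contrast takes exposed cohorts "compared with unexposed cohorts from the same school".
- **Section 3.10 (Data management):** the data file on the TSD server "will not contain identifiers such as names, Feide usernames or national ID numbers". The only code described is the encrypted login name, which is a person-level serial number.
- **Section 4.7 (Access to data):** the investigator team has access to the de-identified final trial dataset.

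**The concern.** The confidentiality section and the analysis section cannot both be followed if they refer to the same file. For class, 4.5 removes the membership itself. For school it removes only the name, so a school code is not ruled out, but no section says that one is kept. Start group is set by school and is not mentioned as a retained variable either. Without school or start group, exposure status at the January and February 2024 waves cannot be assigned, and the same-school cohort comparison cannot be formed.

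Two things are at stake. A data manager who applies 4.5 as written would make the prespecified model impossible to fit, and standard errors that leave out the class level would be too small. A team that keeps class in order to run the SAP would depart from a confidentiality commitment in its own protocol.

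**Working it through.** **1. Is it the same file?** Set side by side, the sections point to one file.

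- 3.10 describes a single data file in TSD, which staff use for analysis.
- 4.7 names the final trial dataset as what the team may access.
- 4.5 rules out disclosing data to others, and 4.8 offers the protocol and the statistical code but no data. No external release is described to which the term in 4.5 could refer instead.
- 3.10 does not list school or class among the items left out, so a fuller working file may be intended. No section says so.

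The parenthesis in 4.5 cannot be a full variable list, because the outcomes must also be in the file. It reads best as the identifying or grouping variables that remain, and class and school are not among them.

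**2. Reproduce the plan's power.** Inputs from 3.7: J = 157 classes in total, n = 15 pupils per class, effect f = 0.16, ICC = 0.05, two-sided 0.05.

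- Noncentrality = sqrt(J·f² / (4·ICC + 4·(1 − ICC)/n)) = sqrt(157 × 0.0256 / (0.20 + 0.2533)) = sqrt(4.0192 / 0.4533) = 2.98
- Noncentral t with 157 − 2 = 155 df gives power 0.8411, which is the stated figure. The inputs are therefore read correctly, and class is the cluster that the plan relies on.

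**3. Consequence if class is dropped and ignored.** This takes a single-timepoint comparison in which whole classes are exposed or not.

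- Pupils: 157 × 15 = 2,355
- Design effect: 1 + (15 − 1) × 0.05 = 1.70
- SE of the difference ignoring class: 2/sqrt(2355) = 0.041 SD
- SE of the difference allowing for class: 2 × sqrt(1.70/2355) = 0.054 SD
- Actual two-sided type I error: 2 × (1 − Φ(1.96/sqrt(1.70))) = 2 × (1 − Φ(1.503)) = 0.133
- A simulation of 79 versus 78 classes of 15 (20,000 runs, naive test) gave 0.134.
- Power computed without the design effect would read 0.973 instead of 0.841.

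**4. Sensitivity to the ICC.** Only 0.05 is in the plan. The other values are assumptions; the smaller ones stand for what may remain after baseline adjustment.

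| Class ICC | Design effect | Type I error if class is ignored |
|---|---|---|
| 0.01 | 1.14 | 6.6% |
| 0.02 | 1.28 | 8.3% |
| 0.05 (plan) | 1.70 | 13.3% |
| 0.10 | 2.40 | 20.6% |

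**5. School level.** Section 2.1 gives 16 schools, so about 2355/16 = 147 participants each. The documents give no school-level correlation. If start group were known but school were not, and school were the only source of clustering, ignoring it would give a type I error of 13.6% at an assumed school ICC of 0.005 and 21.2% at 0.01, using design effect 1 + (147.2 − 1) × ICC.

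**The case against.** The strongest reply is that the final dataset in 4.5 is a stripped file and that analysis uses the TSD file of 3.10, whose exclusion list is shorter. On that view 3.11 itself shows that the authors expect to hold class and school. This is possible, and it is why the point is put as a contradiction to reconcile and not as proof that the model cannot be run. But 4.7 uses the same term for the team's own file, and no section separates the two.

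Some further objections stand in part:

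- **The 13% is conditional.** It requires that 4.5 governs the analysed file, that no class code survives and that clustering is then ignored. No section plans a naive test. In the five-wave model exposure changes over time within pupils, so stable class differences partly cancel. The smaller values in the table may be nearer the truth there.
- **There are fallbacks.** With a school code, errors could be clustered by school, which also covers correlation within classes, or school-by-grade cells could stand in for class. For the February contrast, school is the level that has to be respected in any case. But there are only 16 schools, the code is not promised, and neither fallback is the prespecified four-level model.
- **Silence on start group is weak evidence.** The protocol gives no variable list, and start group might be partly recovered from the timing of the feasibility questionnaires in Figure 2. This part is a request for clarity. It does not affect the contradiction on class.

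**Conclusion.** The concern holds: 4.5 as written removes a variable that 3.11 and 3.7 depend on, and no section available for review restores it in coded form. For school and start group the finding is narrower, namely that their retention is not stated.

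The stated power of 0.8411 is correct on its own inputs and does not change. The type I error in the working (about 13% at the plan's ICC, 6.6% to 8.3% at assumed residual ICCs of 0.01 to 0.02) illustrates what leaving out the class level would cost in a single-timepoint comparison of whole classes. It is not a forecast for the planned model.

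This should be fixed before the analysis file is built. Confidence is medium, because a separate working file may have been intended.

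**What to change.** Reword 4.5 so that school names and recognisable class labels are removed, while the TSD analysis file keeps an arbitrary school code, an arbitrary class code and a start-group indicator, with the key held separately. Record the school and class codes at each wave, since pupils move up a grade between baseline and November 2024. State that these codes are dropped only from any file archived or released outside TSD. Use one term for the analysed file in 3.10, 4.5 and 4.7.

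The cost is one or two protocol sentences and possibly a note to the ethics committee, because 4.5 is a confidentiality commitment. Keeping the codes adds a small re-identification risk, limited by the file staying in TSD with restricted access. No sample size or power figure changes.
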